H. Temporary suspension of Individual Patients

The protocol will allow for temporary suspensions, i.e., transfusion at a higher platelet count threshold than allowed for the randomization arm, if the clinical situation warrants immediate transfusion for certain conditions including: 1) chest-tube insertion; 2) surgical intervention while on ECMO (such as tracheostomy or repair of congenital diaphragmatic hernia); 3) during ECMO circuit change; or 4) in preparation for decannulation. In addition, while patients will be monitored for severe bleeding and/or severe clotting events during this time, they will not have the transfusion strategy permanently discontinued if they develop such an event during the temporary suspension, provided that the severe bleeding/clotting has resolved within the 24 hours of the temporary suspension. If a patient continues to have severe bleeding or severe clotting past the 24 hours of the temporary suspension, the intervention is stopped.

Adherence to the trial protocol must be resumed as soon as possible once these events are controlled or completed. Data monitoring and collection will be unchanged during suspension (including pre-transfusion platelet counts and platelet transfusion volumes), but data on length and justification of suspension will also be collected. Suspensions less than 24 hours will not be considered a breach of adherence to the protocol. After 24 hours of temporary suspension, the patient will have all assigned treatment strategy implications lifted (i.e., no restrictions on the range at which any subsequent platelet transfusions may occur) but will continue to be followed for ascertainment of safety and study outcomes. Temporary suspensions will only necessitate exclusion from analyses for one of the secondary endpoints (#6: proportion of compliant platelet transfusion actions), as explicitly noted in Section 9.B. The safety outcomes will still be followed but will be analyzed as a sub-group (e.g., severe bleeding during temporary suspensions).

9. Outcomes

The objective for the **pilot study** will be to assess the **feasibility** of the full RCT.

A. Primary Outcome

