The primary objective is to assess the separation between the higher and lower platelet threshold arms. Indeed, for a transfusion trial to be successful, there has to be a clinically meaningful separation between the transfusion strategies, to be able to imply causality for the outcome. Since the higher platelet threshold is $<90 \times 10^{9}$ /L and the lower platelet threshold is $<50 \times 10^{9}$ /L, we expect the **separation of the pre-transfusion platelet count (primary outcome) to be at least 30 x10⁹/L**. To assess the separation between both arms, we will collect the pre-transfusion platelet count before each transfusion event.

In addition, we will collect the total daily platelet transfusion dose for a patient while the patient is on ECMO. The average daily dose (in ml/kg/day) will be computed by the research team, by dividing the total platelet transfusion volume by the patient's weight at admission and the number of days on ECMO.

These outcomes will be measured outside of temporary suspensions; that is, transfusions occurring during a temporary suspension are ignored from these analyses.

The primary *safety* outcome, which is assessed in conjunction with the early trial stopping rule, is occurrence of any of the following from the time of randomization (enrollment) to 24 hours after the transfusion strategy threshold was permanently discontinued: progression from no bleeding or minimal bleeding to severe bleeding, according to the BASIC definition (34); severe thrombotic event, according to the NHLBI Hemostasis Clinical Trial Outcomes Working Group (need for circuit change, need for thrombectomy, ischemic stroke, or distal thromboembolism, as diagnosed clinically) (48); death (i.e., all-cause mortality). The primary safety outcome ignores severe bleeding/severe clotting that begins during a period of temporary suspension, but does not ignore deaths that occur during a period of temporary suspension.

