- Proportion of compliant platelet transfusion actions (examples of noncompliance are transfusion given at or above threshold or without any platelet count in the previous 12 hours, excluding transfusions given during a temporary suspension, or transfusion not given within 12 hours of a platelet count below threshold) > 90% (see Appendix F for details);
- Proportion of patients with one or more temporary suspensions not due to preparation for decannulation < 10%;

- 8. Proportion of patients who withdraw from the study and/or are lost to follow-up (i.e., withdraw and/or are missing 90-day mortality assessment) < 6%;
- Proportion of patients with non-platelet transfusion protocol violations (violation of sitespecific management protocol for any aspect besides platelet transfusion threshold compliance) < 5%;
- 10. First instance of progression to severe bleeding or thrombotic outcomes can be adjudicated in > 90% of the patients for whom such an outcome was reported by the site.

Similar to pre-transfusion platelet counts, overall platelet transfusion doses, and progression to severe bleeding and/or clotting, feasibility outcomes 1, 6, and 9, are to be analyzed outside of temporary suspensions.

C. Tertiary Outcomes

Our tertiary outcome is to demonstrate the ability for an adjudication committee to determine the severity of bleeding and/or thrombotic outcomes.

This is similar to the primary safety outcome, except that it does not include mortality in the definition. That is, progression to severe bleeding or a severe clotting event must occur, whether or not there is an all-cause death. We will demonstrate that the recorded data is sufficient for the adjudication of severe bleeding, severe thrombus or both in 90% of enrolled subjects with this outcome reported by the site.

Justification of BASIC and NHLBI definitions of bleeding and thrombosis:

We believe that the BASIC (34) (Table 1) and NHLBI definitions (48) of bleeding and thrombosis provide the most relevant descriptions as they relate to children supported by ECMO. Importantly, central nervous system involvement, a frequent site of bleeding on ECMO, may be captured by a

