Calculation: Adherence % = 100% * (Adherences)/(Adherences + Non-adherences)

Feasibility Criterion 6 Threshold: Adherence > 90%

Statistical Analysis Plan

Protocol Title: ECMO Hemostatic Transfusions in Children

Protocol Version and Date: 1.3.1; July 14, 2023 (BRANY IRB approved July 19, 2023)

SAP Authors: [name] (with reuse of protocol and DCC template language)

SAP Version and Date: 1.0; November 9, 2023

CONFIDENTIAL

Approvals:

Approved By:		
DocuSigned by:	Sutdy PI	
[name]		11/10/2023
N 25066330F4F748A	Title	Date
DocuSigned by:	Study PI	
[name]		11/10/2023
Na891D9374C814C7	Title	Date
DocuSigned by:	Co-I,	
[name]	Statistician	11/10/2023
Nacie D23B98F4BB	Title	Date

Contents

	Abbreviations	v
1	1.1 Purpose of SAP	1 1 1
2	 2.1 Study Objectives	$1 \\ 1 \\ 1 \\ 2 \\ 2 \\ 6 \\ 7 \\ 8$
3	3.1 Overall Study Design	0 0
4	STUDY SUBJECTS AND ANALYSIS POPULATIONS14.1 Eligibility14.2 Populations for Analyses14.2.1 Screening Population14.2.2 Inclusion Population14.2.3 Eligible Population14.2.4 Approached Population14.2.5 Consented Population14.2.6 Intention-to-Treat Population14.2.7 Safety Population1	1 1 1 1 2 2 2
5	GENERAL ISSUES FOR STATISTICAL ANALYSES135.1 Analysis Software135.2 Methods for Withdrawals, Missing Data, and Outliers135.3 Multiple Comparisons and Multiplicity13	$\frac{3}{3}$

	$5.4 \\ 5.5 \\ 5.6$	Planned Subgroups, Interactions, and Covariates	14 14 14
6	INT 6.1 6.2 6.3 6.4 6.5 6.6	CERIM ANALYSES Frequency of and Timepoints for Interim Analysis Stopping Rules for Interim Efficacy Analysis Futility Monitoring in the Interim Analysis Early Trial Termination for Safety Subgroups in the Interim Analysis Blinding in the Interim Analysis	 15 15 15 15 17 17
7	PL 7.1 7.2 7.3 7.4 7.5 7.6 7.7	ANNED ANALYSESDescription of Participant CharacteristicsPrimary Outcome Analysis7.2.1Primary Analysis for Aim 17.2.2Additional AnalysesSecondary Outcomes Analyses (Analyses for Aim 2)7.3.1Primary Analysis for Aim 2Tertiary Outcome AnalysisAdditional Outcome AnalysesTechnical Approaches for Subgroup AnalysesSafety Analyses	 17 17 18 19 19 19 20 20
8	SAI	MPLE SIZE DETERMINATION	21
9	Ref	erences	22
		pendix: INTERIM STOPPING RULE OPERATING CHARACTER- ICS	23
A	Inte	erim stopping rule considerations	23
в			24

Abbreviations

Abbreviation	Definition
AIC	Akaike Information Criterion
APPROACHED	Approached Population; see Section 4.2
BP	Blood Pressure
$\operatorname{CAR}(1)$	Continuous analog of first-order AutoRegressive process

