- Endpoint: $100\% \times (\# \text{ of ITT patients with any reported violations of local non-study-specific circulatory support protocols)/(# of ITT patients)$
- Feasibility threshold: < 5%

(SE10) Adjudication percentage of progression to severe bleeding/thrombotic outcomes

- Outcome: This is defined for each patient in the ITT population (Section 4.2.6) for whom there was any site-reported instance of progression to severe bleeding and/or thrombosis in the acute follow-up period (the **acute follow-up period** consists of the time from randomization through 24 hours past when the transfusion strategy was last applicable). Because any site-reported severe bleeding or severe prognosis is cause to terminate use of the transfusion strategy for that patient, we focus on whether the initial such event can be adjudicated, whether or not additional distinct events were later observed. The patient's outcome is defined as adjudicated if the adjudication panel reached a decision for the initial site-reported event (confirming or overturning the site-level decision for the initial event), and defined as not adjudicated if the panel was unable to reach either a confirmation or overturning decision for the reported event even after requesting additional information from the site
- Endpoint: $100\% \times (\# \text{ of ITT patients with site-reported severe bleeding/thrombotic outcomes for which the adjudication panel was able to adjudicate the patient's first such reported outcome)/(# of ITT patients with site-reported severe bleeding/thrombotic outcomes)$
- Feasibility threshold: > 90%

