2.2.5 Safety Outcome(s)

Many safety outcomes are obtained during the *acute follow-up period*, defined as the period beginning with randomization and ending 24 hours after the permanent discontinuation of the transfusion strategy. The transfusion strategy for a randomized patient is permanently discontinued at the earliest of any of the following five events: (1) per site report, progression to severe bleeding, according to the BASIC definition, and/or severe clotting, and/or death; (2) decannulation from ECMO; (3) twenty-one days post-randomization (as the progression to new bleeding and new thrombosis has plateaued by day 21 and $\approx 95\%$ of the patients will be off ECMO by then); 4) temporary suspension lasting more than 24 hours; or 5) study withdrawal.

The primary safety outcome is defined at the patient level for all patients in the ITT population. It is defined as the occurrence of any of the following during the acute follow-up period: progression to severe bleeding (defined below); progression to severe thrombosis (defined below); death. The outcome is initially site-reported but then is to be adjudicated by the adjudication panel. If the panel determines the outcome criteria were not met, the outcome will be considered not to have occurred. Otherwise, if the panel confirms the criteria were met, or if the panel is unable to reach a determination, the primary safety outcome will be considered to have occurred.

Using the BASIC definition [2], severe bleeding will be defined as:

- 1. Bleeding that leads to at least one organ dysfunction, using PELOD-2 score criteria of organ dysfunction
- 2. Bleeding that leads to hemodynamic instability, defined as an increase in heart rate (HR) by > 20% from baseline or a decrease in blood pressure (BP) by > 20% from baseline (i.e., prior to the bleeding event)
- 3. Bleeding leading to a drop in hemoglobin >20% within 24hr
- 4. Quantifiable bleeding $\geq 5 \text{ mL/kg/hr}$ for $\geq 1 \text{hr}$ (e.g., chest tube)
- 5. Intracranial hemorrhage on computerized tomography (CT) scan or head ultrasound
- 6. Intraspinal bleeding leading to loss of neurologic function below the lesion, nontraumatic intra-articular bleeding leading to decreased range of movement, or intraocular bleeding leading to impaired vision.

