6.4 Early Trial Termination for Safety

Tests of the primary safety outcome will be conducted from the SAFETY population (see Section 4.2.7). Per the DSMB guidance, we increased the planned frequency of comparing the primary safety outcome between treatment arms for the purpose of applying early trial termination criteria. Instead of one interim analysis after 25 enrollments, testing for a difference between treatment arms in the proportion of enrolled patients experiencing the primary safety outcome, a group sequential approach will be taken.

After the adjudication of every 5 new patients who were reported by the site to have had the primary safety outcome, we will conduct a two-sided Fisher's exact test using an alpha threshold of 0.0333.¹ Each test will include those with a known outcome at the time the

¹This p-value threshold was chosen so that, accounting for the varying number of interim tests that may be conducted, the overall type I error rate is close to 0.05. The SAP's Appendix contains a detailed motivation for the 0.0333 threshold at each interim look.

Interim stopping rule example. After every 5 patients with safety outcome, conduct Fisher's exact test at alpha=0.0333. Example below assumes at each test, 50% of patients had safety outcome and enrollment was balanced between Arms A and B

adjudication process is completed (even if for a participant enrolled after the fifth new reported event), with participants for whom the outcome has not yet been determined being excluded until the outcome has been determined. We will test the null hypothesis that the two treatment strategies have the same expected proportion of patients who will experience the primary safety outcome. If a test is significant, we will stop the trial for safety reasons.

Many factors may influence exactly what the stopping rule thresholds are in the trial, such as primary safety outcomes that are overruled by the adjudication panel (expected to be uncommon), the underlying event rate, and the balance of randomization to treatment arms throughout the trial.

Figure 6.4 is an illustrative example of how the rule translates to go/no-go thresholds under one particular set of assumptions:

- At every interim look, there have been equal numbers randomized to each treatment.
- At every interim look, half of the total number of enrolled patients have experienced the primary safety outcome (though the numbers can differ by arm)

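### The SAP's primary safety outcome lacks the protocol's temporary-suspension exception, and parts of the protocol are not aligned with it either, so the events behind the five-patient looks and Fisher tests are not uniquely defined

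*Combined protocol and SAP*

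**What the plan says.** **Protocol v1.4 (April 22, 2024)**

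- Section 9.A, on the primary safety outcome: "The primary safety outcome ignores severe bleeding/severe clotting that begins during a period of temporary suspension". Deaths in a suspension are kept.
- Section 9.B agrees: "progression to severe bleeding and/or clotting, feasibility outcomes 1, 6, and 9, are to be analyzed outside of temporary suspensions".
- Section 8.H says of children in a suspension: "The safety outcomes will still be followed but will be analyzed as a sub-group (e.g., severe bleeding during temporary suspensions"). It also says: "Temporary suspensions will only necessitate exclusion from analyses for one of the secondary endpoints", naming number 6.
- Section 8.G ends the assigned strategy for severe bleeding or clotting only when the event falls outside a suspension. Section 8.H keeps the strategy going if such an event resolves within the 24 hours.
- The adjudication text in 9.A starts a review once five new patients have any reported severe event and says the intervention stops. It has no suspension exception. The lists of discontinuation events in 11.A and in 11.B (Clinical Adverse Events) have none either.

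**SAP 1.0 (November 9, 2023)**

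- The title page gives "Protocol Version and Date: 1.3.1; July 14, 2023".
- Section 2.2.5, on the primary safety outcome: "It is defined as the occurrence of any of the following during the acute follow-up period". The listed events are severe bleeding, severe thrombosis and death, with no suspension exception.
- Section 6.4 runs the Fisher test at 0.0333 as follows: "After the adjudication of every 5 new patients who were reported by the site to have had the primary safety outcome". Section 7.7 repeats the test at the end of the study. Neither adds an exception.
- Section 2.2.2 (SE10): "Because any site-reported severe bleeding or severe prognosis is cause to terminate use of the transfusion strategy for that patient". Again there is no exception.

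**The concern.** SAP 7.7 makes this the trial's only planned safety hypothesis. A crossing pauses the trial for DSMB review (protocol 10.C, Interim Analysis); SAP 6.4 says the trial stops.

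The definition enters the rule twice. It decides which children count as events in the 2x2 table, and it decides when the fifth, tenth and later event is reached, and so when a look takes place. A programmer working from the SAP as written would count a severe bleed that began during a circuit change or a surgical procedure. A programmer working from protocol 9.A would not. The same data could therefore give the DSMB looks on different dates and, at the margin, different results.

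The pilot's rate for this outcome is also a stated input to the design of the full trial (protocol 10.A). The proposed primary outcome of that trial ignores suspension-onset events (Appendix A).

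**Working it through.** **1. Is the exception supplied anywhere else in the SAP?** Sections 2.2.2, 2.2.3, 6.4, 7.7 and the Appendix code contain none. Section 3.1 refers to the protocol for suspensions, but in connection with transfusion management and not the outcome.

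**2. Reproducing the plan's own figures.** The SAP simulation has N=50, simple 1:1 allocation, a look at every fifth event plus a final look, and two-sided Fisher p ≤ 0.0333. Re-coded with 2,000 trials at each event rate from 0.20 to 0.80, it gives an average type I error of 0.0504; the SAP states 0.0502. The example boundaries in protocol 10.C also reproduce:

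| n | Lower v higher arm | p |
|---|---|---|
| 10 | 5/5 v 0/5 | 0.0079 |
| 20 | 8/10 v 2/10 | 0.0230 |
| 30 | 11/15 v 4/15 | 0.0268 |
| 40 | 14/20 v 6/20 | 0.0256 |
| 50 | 17/25 v 8/25 | 0.0227 |

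**3. One lower-arm event ignored, final test.** The final test takes place whatever the event count. 17/25 v 8/25 becomes 16/25 v 8/25, and p goes from 0.0227 to 0.0465. The first crosses 0.0333 and the second does not.

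**4. One lower-arm event ignored, interim looks.** At n=10, 20, 30 and 40 the event totals fall from 5, 10, 15 and 20 to 4, 9, 14 and 19. No look is then due until the next event. Add one child per arm, one of whom has that event:

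| Starting n | Next event in lower arm | Next event in higher arm |
|---|---|---|
| 10 | 5/6 v 0/6, p=0.015 | 4/6 v 1/6, p=0.242 |
| 20 | 8/11 v 2/11, p=0.030 | 7/11 v 3/11, p=0.198 |
| 30 | 11/16 v 4/16, p=0.032 | 10/16 v 5/16, p=0.156 |
| 40 | 14/21 v 6/21, p=0.029 | 13/21 v 7/21, p=0.122 |

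The look is delayed, and its result then depends on where the next event falls. These values treat the reclassified child as a determined non-event. If that child's outcome is still pending and the child is left out of the test, p is 0.002, 0.009, 0.012 and 0.013 (lower arm) or 0.080, 0.086, 0.076 and 0.063 (higher arm). The conclusions are the same.

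**5. How often the two definitions would disagree.** The documents do not say how many children have a suspension-onset event as their only qualifying event. Assume K = 1, 2 or 4 of 50. Four is the most children with a non-decannulation suspension if SE7 (below 10%) is met, since 4/50 = 8% passes and 5/50 = 10% fails. Decannulation suspensions are not capped. Each simulated trial was run twice on the SAP schedule, counting and then ignoring the K children, with looks rescheduled (20,000 trials per row):

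| Event rates | K | Crosses, counted | Crosses, ignored | Disagree |
|---|---|---|---|---|
| 65% v 65% | 1 | 5.5% | 5.6% | 3.5% |
| 65% v 65% | 2 | 5.3% | 5.3% | 4.3% |
| 65% v 65% | 4 | 5.3% | 5.7% | 6.1% |
| 80% v 50% | 1 | 54.4% | 50.6% | 12.0% |
| 80% v 50% | 2 | 55.4% | 47.6% | 16.0% |
| 80% v 50% | 4 | 54.9% | 40.2% | 24.1% |

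The 65% is the planning figure in Appendix A. The 80% v 50% difference is an assumption.

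**The case against.** The strongest reply is that this is version lag. The SAP predates v1.4, is silent on suspension-onset events rather than opposed to the exception, and refers readers to the protocol for conduct. One coordinating center runs the analyses, with dual programming or code review, so two analysts holding different documents is hypothetical. That probably explains the mismatch, but it does not settle it: the documents include no SAP aligned with v1.4, and independent programming from the same SAP text would reproduce the same omission. Deferring to the protocol does not settle it either, because the batch trigger in 9.A has no exception.

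It is also fair to say that the sizes are mostly assumption. K=4 tied to SE7 is an extreme case, in which every child with a non-decannulation suspension has a suspension-onset event as the only qualifying one. Many disagreements come late. At 80% v 50% with K=1, about 53% of them involve a crossing at n ≥ 45, where little enrollment is left to pause, and at n=50 none is left.

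A reader might infer more than the documents support:

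- *That the SAP expressly counts these events.* It does not say so; it only lacks the exception.
- *That the 0.0333 threshold is miscalibrated.* It reproduces, and crossing under equal rates stays at 5.3-5.7% with either definition.
- *That one reclassified child reverses an interim look.* 7/10 v 2/10 would give p=0.070, but with nine events no look is due.
- *That 8.H contradicts 9.A.* Its restrictive sentence concerns secondary endpoints, so the clear conflict is with 9.B, which names items 1, 6 and 9. Its sub-group sentence fits 9.A if the events are left out of the test and summarized separately.

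**Conclusion.** The point holds as a conflict between the two documents, compounded by uneven wording inside the protocol. As written, the SAP tests an outcome that differs from the current protocol's, and the five-patient count that schedules the tests has the same gap.

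The size is illustrative. Disagreement on crossing is about 3-6% of trials with equal 65% rates and about 12-24% at 80% v 50%, for K from 1 to 4. Both K and the 80% v 50% difference are assumed, and K was drawn at random from the children with events. Under that true difference, ignoring these events lowers the crossing rate from about 54-55% to 51%, 48% or 40%. Type I error is not the issue. Under the current protocol the consequence of a crossing is a pause and DSMB review, not automatic termination.

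This should be corrected. It does not undermine the design of the stopping rule.

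**What to change.** 1. Update the SAP to protocol v1.4 and state one definition of the primary safety outcome in protocol 9.A (both the definition and the adjudication batch trigger), protocol 10.C, and SAP 2.2.5 and 6.4. The same events should then feed the five-patient batch, every interim Fisher test and the final test. The current protocol's definition is the one in 9.A. If the sponsor prefers to count suspension-onset events, 9.A and 9.B must change instead.
2. If any interim test has been run, record which definition it used.
3. Report suspension-onset severe events separately by arm to the DSMB in closed session, descriptively and without a test.
4. Align pause (protocol 10.C) with stop (SAP 6.4), and reconcile 8.H with 9.B on which endpoints exclude suspensions.
5. Reconcile the passages on ending the strategy for an event in a suspension: protocol 8.G, 8.H, 9.A, 11.A and 11.B, and SAP 2.2.2 (SE10) and 2.2.5. No clinical rule is proposed here. These passages also set where the acute follow-up period ends.

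Optional tidying: say which time marks onset for a circuit clot that leads to a circuit change, and use the same intracranial-hemorrhage wording in both documents.

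**Cost.** A short SAP amendment and a few protocol edits. Episode start and suspension length are already to be recorded. The case report forms are not in the documents, so check that they allow an event to be placed inside or outside a suspension. The downside of keeping the 9.A definition is that suspension-onset events stay out of the tested comparison; the separate report by arm is meant to cover that.

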The primary outcome will be the proportion of patients who progress from no bleeding or minimal bleeding to severe bleeding and/or severe thrombosis, ignoring events that begin during a period of temporary suspension.

Using the BASIC definition plus one additional element, severe bleeding will be defined as:

- 1) Bleeding that leads to at least one organ dysfunction, using PELOD-2 score criteria of organ dysfunction
- Bleeding that leads to hemodynamic instability, defined as an increase in HR by > 20% from baseline or a decrease in BP by > 20% from baseline (i.e., prior to the bleeding event)
- 3) Bleeding leading to a drop in hemoglobin > 20% within 24hr
- 4) Quantifiable bleeding \geq 5 mL/kg/hr for \geq 1hr (e.g., chest tube)
- 5) New and/or expanding intracranial hemorrhage on CT scan or head ultrasound
- 6) Intraspinal bleeding leading to loss of neurologic function below the lesion, nontraumatic intra-articular bleeding leading to decreased range of movement, or intraocular bleeding leading to impaired vision.

ECMO Hemostatic Transfusions in Children (ECSTATIC) Study Protocol – version 1.4 – April 22, 2024

Severe thrombotic events will be defined according to the NHLBI Consensus Conference as circuit clot leading to circuit change, need for thrombectomy, ischemic stroke, or distal thromboembolism.

As this is an open-label trial, the primary outcome will be **adjudicated** by an independent central committee, blinded to the allocation group. This committee, composed of three members, will determine if the bleeding was the primary cause of organ dysfunction, hemodynamic instability, acute anemia, loss of spinal function, articular range of motion, or impaired vision.

Secondary Outcomes

The secondary outcomes will be:

- 1) hemorrhagic complications according to the ELSO definition
- 2) thrombotic complications according to the ELSO definition
- 3) blood product exposure, defined as the total number of transfusions (red blood cell, plasma, platelets, cryoprecipitate)
- 4) duration of ECMO, defined as 90-day ECMO-free days
- 5) length of stay, defined as the 90-day PICU-free days
- 6) functional outcome at hospital discharge, defined as the discharge Pediatric Overall Performance Category (POPC) and Pediatric Cerebral Performance Category (PCPC)
- 7) all-cause mortality on ECMO, at 28 days, and at 90 days.

Sample Size

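### The protocol drops severe bleeds and clots that begin in a temporary suspension from the safety test, the SAP counts them, and the exclusion depends on the assigned arm

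*Combined protocol and SAP*

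**What the plan says.** The documents give different answers on whether a severe event that begins in a suspension counts.

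- **Protocol 9.A (Primary Outcome), v1.4:** "The primary safety outcome ignores severe bleeding/severe clotting that begins during a period of temporary suspension". Deaths in a suspension still count. This is the outcome that drives the early stopping rule.
- **Protocol 9.B (Secondary Outcomes), closing paragraph:** "progression to severe bleeding and/or clotting, feasibility outcomes 1, 6, and 9, are to be analyzed outside of temporary suspensions". This agrees with 9.A.
- **Protocol 8.H (Temporary suspension):** "Temporary suspensions will only necessitate exclusion from analyses for one of the secondary endpoints", namely number 6. This disagrees with 9.A and 9.B. The same section says that safety outcomes in suspensions are still followed and are analysed as a sub-group.
- **SAP 2.2.5 (v1.0, written to protocol 1.3.1):** the primary safety outcome is any severe bleed, severe thrombosis or death in the acute follow-up period, with no exception for suspensions. SAP 6.4 and 7.7 test that outcome.

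Protocol 8.H describes a suspension as "transfusion at a higher platelet count threshold than allowed for the randomization arm". It adds: "If a patient continues to have severe bleeding or severe clotting past the 24 hours of the temporary suspension, the intervention is stopped". No text then turns that event into a counted one.

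The proposed full trial (protocol Appendix A, Primary Outcome) carries the exclusion forward, "ignoring events that begin during a period of temporary suspension".

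**The concern.** Whether an event is ignored depends on something that happens after randomization, is decided by clinicians who know the arm, and is defined by the arm's own threshold. Transfusing before a procedure at a count of 50-89 departs from the assigned strategy in the lower arm but follows it in the higher arm. If the same severe procedural bleed then occurs in both children, it may count in one arm and not in the other.

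An event that begins in a suspension and is still severe past 24 hours ends the strategy, yet under 9.A it is not counted unless the child dies within the safety window. It then enters neither the five-patient adjudication batch nor the Fisher test. The sub-group analysis in 8.H does not feed the pause rule.

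This is the pilot's only formal safety test. Its event rate is meant to inform a non-inferiority trial, where lost events that narrow the difference between arms make non-inferiority easier to declare.

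**Working it through.** **1. Where the arms differ.** Transfusion needs no suspension below 50 in the lower arm and below 90 in the higher arm (protocol 8.A). The counts at which only the lower arm needs one are therefore 50-89. Protocol 5.B gives a median pre-transfusion count on ECMO of 72 (IQR 54-88). That interquartile range lies wholly inside the band, so at least half of those historical counts do too. They are not specific to procedures.

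**2. The plan's own boundaries.** Two-sided Fisher test at 0.0333, equal arms, half the patients with an event (protocol 10.C). All five reproduce:

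| n | Lower v higher | p |
|---|---|---|
| 10 | 5/5 v 0/5 | 0.0079 |
| 20 | 8/10 v 2/10 | 0.0230 |
| 30 | 11/15 v 4/15 | 0.0268 |
| 40 | 14/20 v 6/20 | 0.0256 |
| 50 | 17/25 v 8/25 | 0.0227 |

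**3. One ignored lower-arm event at the final test.** The child stays in the denominator: 16/25 v 8/25 gives p = 0.0465, above 0.0333, so there is no signal. If one event is dropped from each arm, 16/25 v 7/25 gives p = 0.0222 and the signal stands.

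**4. One ignored lower-arm event at an interim look.** Looks are held only at each fifth event. At n = 20, 30 or 40, dropping one leaves 9, 14 or 19 events, so no test is held until the next event. Suppose the next patient enrolled has that event:

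| Boundary | Event in lower arm | Event in higher arm |
|---|---|---|
| n = 20 | 8/11 v 2/10, p = 0.030 | 7/10 v 3/11, p = 0.086 |
| n = 30 | 11/16 v 4/15, p = 0.032 | 10/15 v 5/16, p = 0.076 |
| n = 40 | 14/21 v 6/20, p = 0.029 | 13/20 v 7/21, p = 0.063 |

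The pause is delayed in the first case and not reached at that look in the second.

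**5. Operating characteristics.** The simulation in the SAP appendix was repeated: N = 50, simple 1:1 allocation, a look at every fifth event and at the end. Average overall type I error over p = 0.20 to 0.80 was 0.0494, against the SAP's 0.0502, which is within simulation error. Each arm's event probability was then multiplied by (1 - ignored share). For example, a 10% share turns 0.65 into 0.65 x 0.90 = 0.585. There were 8,000 trials per scenario.

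The 65% rate comes from Appendix A, Sample Size. The ignored shares (0-20% lower, 0-10% higher) and the harm scenario of 80% lower v 50% higher are **assumptions**. The shares apply to all primary safety events, net of children who die in the window and so count anyway.

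| Ignored: lower, higher | 65% both: lower worse | 65% both: higher worse | 80% v 50%: lower-arm harm signalled |
|---|---|---|---|
| 0, 0 | 2.8% | 3.1% | 55% |
| 10%, 10% | 3.0% | 2.7% | 43% |
| 10%, 5% | 1.7% | 4.6% | 36% |
| 10%, 0 | 1.2% | 5.9% | 31% |
| 20%, 10% | 1.2% | 7.1% | 23% |
| 20%, 0 | 0.4% | 13.2% | 15% |
| 0, 10% | 6.5% | 1.1% | 68% |

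Equal losses leave the null error roughly symmetric and cost sensitivity. Unequal losses tilt the test toward whichever arm loses more events.

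**The case against.** Several points on the other side stand.

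- **Direction is not shown.** A reader might infer that the rule removes events mainly from the lower arm. No section gives suspension or event rates by arm. The rule also drops clotting. Circuit change is both a suspension reason (8.H) and, when caused by a circuit clot, a severe thrombotic event, and the protocol's background links platelet transfusion to thrombosis, so those losses could fall on the higher arm. SAP 2.2.2 (SE7) also says a suspension counts even if no above-threshold transfusion was given, so one can be declared for a procedure in either arm.
- **The 24-hour rule is not a self-contradiction.** A reader might infer one because a persistent bleed ends the strategy but is not scored. Ending the strategy and scoring an event are separate matters: protocol 8.G lists several stopping reasons, such as decannulation and withdrawal, that are not safety events. What remains is a questionable scoring choice.
- **Interim p-values.** Recomputing the interim boundaries with one event fewer (for instance 7/10 v 2/10, p = 0.070) describes looks the plan would not hold.
- **Frequency.** Preparation for decannulation is a listed reason, but 8.H allows a suspension only when the clinical situation warrants it, so near-universal suspension cannot be assumed. Other suspensions are targeted below 10%, at most 4 of 50 patients (4/50 = 8%; 5/50 = 10% fails). Decannulation suspensions are outside that target.
- **Other safeguards.** Deaths count, serious adverse events are reported regardless of relatedness, and the DSMB can recommend stopping independently of the rule. SAP Section 8 says the trial is not powered for this outcome, and the Appendix A design is open to revision.

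These points limit the size and direction of the concern. They do not remove the conflict between the documents or the dependence on arm. Under the SAP as written the bias does not arise, but v1.4 is the later document, and aligning the SAP to it would bring the exclusion into the test.

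**Conclusion.** The concern holds as a conflict between the documents plus an avoidable weakness in the v1.4 definition. Whether the loss is lopsided, and which way, cannot be settled from the documents. A lean toward the lower arm is plausible for procedural bleeds at counts of 50-89.

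The directly applicable result is at the final n = 50 boundary, where a single ignored lower-arm event removes the signal. At interim looks the effect is mainly a delay to the next fifth event. The simulated losses of sensitivity depend wholly on the assumed shares and rates and show a range, not a forecast.

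**What to change.** Reconcile protocol 8.H, 9.A and 9.B with SAP 2.2.5 by keeping the SAP's event definition:

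1. For the pause rule and the final safety test, count all severe bleeding and clotting in the acute follow-up period, whatever the suspension status. State this in 9.A and 9.B, and make it explicit in SAP 2.2.5 and 6.4.
2. Send these events to the adjudication committee in the same batches of five.
3. Report the suspension-excluded version and the suspension-period events by arm to the DSMB as supportive.

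At minimum, run the all-events test beside the excluded version at each look, and name in advance which one governs the pause.

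The change concerns scoring only; no rule on suspending or stopping the strategy needs to change. SAP 2.2.5's list of discontinuation events lacks the suspension proviso found in protocol 8.G, so the edit should say that counting an event does not by itself decide whether the strategy ends, and those two lists should be reconciled.

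The cost is a text amendment. Data collection already continues unchanged in suspensions (8.H). Some procedural bleeds will be counted, the committee will see somewhat more cases, and looks will come slightly earlier.
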